4.2.7. Subpopulations

No analyses of subgroups of subjects are planned.

4.2.8. Withdrawals, Dropouts, Loss to Follow-up

Any subject who wishes to voluntarily discontinue study drug or withdraw from participation in the study for any reason is entitled to do so without obligation. IP may be discontinued (insert removed) and any subject may be discontinued from study participation at any time during the study at the discretion of the Investigator or the Sponsor for any reason.

In the event that study discontinuation of a randomized subject is necessary, the Investigator should make every attempt to have the subject complete Visit 7 assessments as soon as possible. The reason for premature discontinuation should be recorded in the subject chart and entered in the eCRF.

Subjects who withdraw will not be replaced.

4.2.9. Missing, Unused, and Spurious Data

If the start date of an AE is partially or completely missing, the date will be compared as far as possible with the date of the start of administration of study drug. The AE will be assumed to be treatment-emergent if it cannot be definitively shown that the AE did not occur or worsen during the treatment-emergent period (worst case approach). The imputed dates will only be used to classify events as treatment emergent and will only be used in the table analyses. Listings will display the available date data.

The following general rules will be used:

- If the start day is missing but the start month and year are complete, an AE will only be excluded as being treatment-emergent if the start month/year is before the month/year

Sponsor:	Ocular Therapeutix, Inc.		
Protocol:	OTX-DED-2020-201		
Document Version No.:	V1.0	Document Date:	11NOV2021

of study drug administration or if the date of resolution is before study drug administration.

- If the start day and month are missing but the start year is complete, an AE will only be excluded as being treatment-emergent if start year is before the year of study drug administration or if the date of resolution is before study drug administration.
- If the start date is completely missing, an AE will be considered treatment-emergent unless the date of resolution is before study drug administration.

4.2.9.1. Imputation Method for Primary Efficacy Endpoints

To impute missing, Markov Chain Monte Carlo (MCMC) multiple imputation (MI), Fully Conditional Specification multiple imputation (FCS MI) and LOCF methods will be used.

For MI, we will have below phases:

1. Imputation Phase: in this phase, the missing data will be imputed using SAS PROC MI and a complete data set will be created. This process of imputation will be repeated 25 times. Therefore, 25 compete datasets will be created. In this phase, treatment group, baseline value, and post-baseline visits will be included in multiple imputation model.
2. Analysis Phase: each of the 25 complete data sets will be analyzed independently using desired statistical method (e.g. ANCOVA for primary efficacy analysis).
3. Pooling Phase: in this phase the estimates obtained from each analyzed complete dataset from phase 2, will be combined using PROC MIANALYZE.

The primary analyses of efficacy data will use MCMC MI methodology to impute missing data. The expectation and maximization (EM) algorithm will be used to estimate the mean vector and the covariance assuming a missing at random (MAR) distribution. The MAR distribution assumes the probability that a value is missing does not depend on the true values of the missing items. The imputation phase will create 25 copies of the dataset which will contain different estimates of the missing values. The 25 complete datasets will then be analyzed to produce several sets of parameter estimates and standard errors, which will then be pooled to create a single set of results.

Last observation carried forward (LOCF) method and Fully Conditional Specification multiple imputation (FCS MI) with 200 burn-in iterations and 25 times of imputation under the assumption of missingness at random will be used for sensitivity analyses (Section 4.7.2).

Sponsor:	Ocular Therapeutix, Inc.		
Protocol:	OTX-DED-2020-201		
Document Version No.:	V1.0	Document Date:	11NOV2021

4.2.10. Visit Windows

Visit windows will be calculated based on the Schedule of Assessments in Table 1. Any visits or procedures performed outside the scheduled visits will be documented in the Unscheduled Visit page of the eCRF. Although there is a visit window around the expected visit date, nominal visits will be used for the per-visit analyses.

4.3. Interim Analyses

An interim analysis was not planned for this study.

4.4. Subject Disposition

A summary of subject disposition will be tabulated, including the number screened, screened failure, and procedural screen failures will be presented. Subjects are considered procedural screen failures if the investigator is unsuccessful at placing the OTXDED or HV intracanalicular ophthalmic insert in both eyes (i.e. neither eye has an insert). Procedural screen failures will be exited from the study at that time, and will be included in the disposition tables as 'randomized, not treated'. Subjects will be followed per protocol if the investigator successfully places one insert.

The number and percentage of subjects included in each of the analysis populations (ITT, mITT, PP, Safety) will be presented by treatment groups and overall. Subject disposition events including randomization, treated, completed study, withdrawal prior to completing the study, and reasons for withdrawal will be summarized by treatment groups and overall.

A by-subject listing of study completion information, including the reason for premature study withdrawal, if applicable, will be presented.

4.5. Demographic and Baseline Characteristics

Baseline and demographic information will be summarized for the mITT population using descriptive statistics. Demographic characteristic information will include Age (year), Age categories (<65, ≥65), Gender (Male, Female), Ethnicity (Hispanic or Latino, Not Hispanic or Latino), and Race (White, Black or African American, Asian, American Indian or Alaska Native, Native Hawaiian or Other Pacific Islander, Unknown, Other).

Demographic and Baseline data will be provided in data listings.

Sponsor:	Ocular Therapeutix, Inc.		
Protocol:	OTX-DED-2020-201		
Document Version No.:	V1.0	Document Date:	11NOV2021

4.5.1. Baseline Ocular Assessments

The following baseline assessments will be presented using descriptive statistics for mITT population by treatment group and overall.

The assessments below will be assessed:

1. Bulbar conjunctival hyperemia (worst zone, Nasal, Temporal, Frontal, Total of 3 zones)
2. Eye Dryness Severity (VAS) Score
3. Eye Dryness Frequency (VAS) Score
4. Investigator assessment of bulbar conjunctival hyperemia
5. Corneal Fluorescein Staining (tCFS) by study eye
6. CFS sub-regions using NEI scale by study eye
7. OSDI total score (0-100) and the score of its three domains
8. SPEED Total Score (0-28)
9. Best Corrected Visual Acuity (BCVA) LogMAR Score
10. IOP Measurement (mmHg)
11. Unanesthetized Schirmer's Test

4.5.2. Ocular and Non-Ocular Medical History

Medical history, including ocular medical history, will be coded using MedDRA Version 24.0 – Mar 2021. Non-ocular medical history will be summarized in the mITT population by system organ class (SOC) and preferred term (PT) by treatment group and overall. SOC will be sorted alphabetically. PT will be sorted by descending frequency overall within each SOC. Subjects with a particular medical history event or medical history class will be counted once at the PT level and once at the SOC level. Ocular medical history will be summarized at the eye and subject levels by treatment group and overall, for the mITT population with separate summaries for the study eye and non-study eye.

Data listings will be provided for medical history as well.

4.6. Treatment Exposure

Details of study drug administration, including duration of treatment will be tabulated and presented for the Safety population. The duration of exposure will be calculated in days as latest date investigator confirms insert is not present in either eye minus date of the earliest insertion in either eye plus 1 and summarized using descriptive statistics by treatment group and

Sponsor:	Ocular Therapeutix, Inc.		
Protocol:	OTX-DED-2020-201		
Document Version No.:	V1.0	Document Date:	11NOV2021

overall. Treatment exposure for subjects who discontinue the study prior to the insert no longer being present in both eyes, will be calculated in days as date of last insert visualization in either eye minus date of the earliest insertion in either eye plus 1. In addition, treatment exposure for subjects who discontinue the study prior to the insert no longer being present in both eyes will be set to the longest observed insert exposure as an additional analysis.

All dosing information will be presented in a data listing.

4.7. Efficacy Evaluation

The efficacy summaries and analyses will be presented for both study and non-study eyes.

The Primary efficacy analysis of the bulbar conjunctival hyperemia will be conducted using the mITT and PP populations.

4.7.1. Primary Analyses

For the primary efficacy endpoint analyses of change from baseline in photographic assessment of bulbar conjunctival hyperemia (evaluated by central reading center) worst zone in the study eye at Visit4 (Day 15) (as defined in section 2.6.1.1), the following modeling and analyses will be performed on mITT population, observed data:

An analysis of covariance (ANCOVA) model will be run to estimate least square (LS) means treatment. This model will include the baseline value as a covariate for adjustment and treatment group as the sole factor. Least square means will be used to make treatment comparisons using Dunnett's adjustment for multiple comparisons to a control. Statistical significance of treatment differences will be determined using a two-sided significance level of $\alpha = 0.05$.

In the ANCOVA model, LS means treatment group comparison of OTX-DED 0.2 mg to HV, OTX-DED 0.3 mg to HV, and Overall OTX-DED (combined OTX-DED 0.2 mg and OTX-DED 0.3 mg using sample size weights of OTX-DED 0.2 mg and OTX-DED 0.3 mg groups as coefficients for the parameters) to HV will be reported. Unadjusted treatment group analyses using two-sample t-test and Wilcoxon rank sum test will be run on these treatment group combinations.

Each bulbar conjunctival hyperemia zone (Nasal, Temporal, and Frontal) and the Total of the three zones in study eye will be analyzed in a manner similar to the primary efficacy variable as described above.

The same analyses will be done for the non-study eye. For non-study eye, the worst zone similar to worst zone in study eye (details in section 2.6.1.1) will be independently determined using photographic assessment bulbar conjunctival hyperemia in non-study eye at baseline.

Sponsor:	Ocular Therapeutix, Inc.		
Protocol:	OTX-DED-2020-201		
Document Version No.:	V1.0	Document Date:	11NOV2021

The primary efficacy endpoints will also be analyzed on PP population.

4.7.2. Sensitivity Analyses

To determine robustness of results, the sensitivity analyses will be performed for the primary efficacy endpoint, bulbar conjunctival hyperemia at Visit4 (Day 15), on the mITT and PP populations by using:

1. MCMC MI
2. last observation carried forward (LOCF)
3. FCS MI.

As sensitivity analyses, LOCF will be analyzed in a manner similar to the primary efficacy variable (details in section 4.7.1). MCMC MI and FCS MI will be analyzed in a manner similar to the primary efficacy variable (details in section 4.7.1), however, for treatment comparisons, least square means will not be adjusted for multiple comparison and for the unadjusted treatment group comparisons, only t-test will be used.

4.7.3. Secondary Analyses

The below secondary efficacy endpoints will be analyzed in a manner similar to the primary efficacy variable using ANCOVA model of change from baseline using observed data:

1. Severity of eye dryness score at Visit 4 (Day 15) and other post-baseline visits,
2. Frequency of eye dryness score at Visit 4 (Day 15) and other post-baseline visits,
3. Investigator assessment of bulbar conjunctival hyperemia in worst zone, Nasal, Temporal, Frontal zones, and Total at each post-baseline visit,
4. Total corneal fluorescein staining (tCFS) and CFS sub-regions at each post-baseline visit.

In addition, sensitivity analyses done for the primary efficacy endpoint (section 4.7.2) will also be performed on severity and frequency of eye dryness scores, investigator assessment of bulbar conjunctival hyperemia, tCFS, and CFS sub-regions endpoints.

The below secondary efficacy endpoints will be analyzed using ANCOVA model of change from baseline at each post-baseline visit similar to primary efficacy endpoint analysis (section 4.7.1) using observed data:

5. Ocular Surface Disease Index questionnaire (OSDI©) at each post-baseline visit (total score, each of the three domains, and individual questions) and
6. SPEED questionnaire (overall score and individual questions), CFB at each post-baseline visit will be analyzed

Sponsor:	Ocular Therapeutix, Inc.		
Protocol:	OTX-DED-2020-201		
Document Version No.:	V1.0	Document Date:	11NOV2021

All the secondary endpoints will be analyzed on mITT and PP populations; therefore, related summary tables will be reported for both mITT and PP populations.

4.7.4. Exploratory Analyses

Ease of insertion as assessed by the Investigator at Visit 2 or Visit 2B, presence of OTX-DED or HV insert and ease of visualization as assessed by the Investigator at all post-baseline visits will be summarized using discrete statistics (number and percentage) and will be tested between treatment groups (OTX-DED 0.2 mg to HV, OTX-DED 0.3 mg to HV, and Overall OTX-DED (combined OTX-DED 0.2 mg and OTX-DED 0.3 mg) to HV). To analyze ease of insertion as assessed by the Investigator and ease of visualization as assessed by the Investigator, the Pearson Chi-squared statistic will be used. To analyze presence of insert, Fisher's exact Test will be used, and Clopper-Pearson method will be used to calculate 95% confidence interval of the proportion of subject with presence of insert; to calculate 95% confidence interval of the proportion difference, the Chan and Zhang (1999) method will be used.

The Schirmer Test without anesthesia will be summarized using descriptive statistics by treatment group and overall and it will be analyzed using ANCOVA model of both change from baseline and absolute value at each post-baseline visit similar to primary efficacy endpoint analysis (section 4.7.1) using observed data.

The exploratory analyses will be done on mITT populations

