8.4.1 Visit 1 (14 ±2 days prior to Day 1) Screening/Baseline Visit

Note: The Screening Visit can be split into two (2) visits in rare cases, but both visits must be within the allowable window.

- Informed consent
- Demographics
- Medical/ophthalmic history
- Record concomitant medications
- VAS Severity and Frequency for Eye Dryness ([Appendix 2](#))
- OSDI ([Appendix 3](#))

- SPEED assessment ([Appendix 4](#))
- BCVA assessment ([Appendix 8](#))
- Slit lamp biomicroscopy (including punctum assessment) ([Appendix 9](#))
- Investigator Rated Assessment of Bulbar Conjunctival Hyperemia ([Appendix 5](#))
- CFS ([Appendix 7](#))
Note: Wait 15 minutes prior to conducting unanesthetized Schirmer test
- Unanesthetized Schirmer
- IOP
- Dilated fundus exam
- Determine Eligibility
- Dispense artificial tears (as needed and not to be administered within 2 hours of clinic visit.)
- Dispense Daily Subject Diary for Artificial Tear Use (as needed) ([Appendix 14](#))

8.4.2 Visit 2 Insertion/Day 1

- Record concomitant medications
- Record AEs*
Note: Any signs, symptoms or conditions captured prior to the insertion of IP, will be recorded as medical history.
- Collect and review Subject Daily Diary for Artificial Tear Use (if applicable)
Note: Subjects using rescue AT > 3x/day for 3 consecutive days will be ineligible for randomization.
- VAS Frequency and Severity for Eye Dryness
- OSDI
- SPEED assessment
- Conjunctival Hyperemia Photography ([Appendix 6](#))
- BCVA assessment
- Slit lamp biomicroscopy, including punctum evaluation
- Investigator Rated Assessment of Bulbar Conjunctival Hyperemia
- CFS
- IOP
- Punctum Size Assessment
- Urine pregnancy test (if applicable must be performed prior to treatment)
- Determine Eligibility for Insertion
- Randomization
- OTX-DED or HV Insert Placement ([Appendix 11](#))*

Note: If placement is only successful in one eye, the items with the asterisk should be performed on the same day. Subjects should be asked to return within 0-3 days to attempt insertion in the other eye. At the return visit, items with an asterisk should be performed on the second eye, and the AE review, Ease of Insertion Assessment and Tear film PK for the second eye should only be performed if the second eye has a successful insertion.

- Ease of Insertion Assessment*
- Tear film PK by Schirmer (to be collected 1 hour (\pm 30 minutes), 2 hours (\pm 30 minutes) and 4 hours (\pm 30 minutes) post-insertion)* ([Appendix 10](#))

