Appendix 11 OTX-DED or HV Insert Suggested Placement Technique

The following is the suggested placement technique and it can be modified based on investigator's medical judgment.

[figure not shown]
1. Apply lateral pressure to elongate the canalicular system. Pull the skin near the punctum down and temporally. A technician may assist if needed.

[figure not shown]
2. Dilate using the punctal dilator in towards the nose, ensuring the system is elongated. Dilate through the punctum deeper into the canaliculus, dilate for depth, as well as width. If desired, rotating the dilator in a spinning motion may help with the dilating process.

3. Dry the surface around the punctal opening using an ophthalmic sponge. More than one sponge may be necessary to ensure adequate drying of area. A technician may assist if needed.

[figure not shown]
4. Grasp OTX-DED or HV insert with forceps and insert at a slight angle towards the nose. Aim for 70% of insertion within the first motion. Use forceps to tap or push insert the remainder of the way in. The insert should sit slightly beneath the punctal opening.

Note: Excessive squeezing of OTX-DED or HV may cause deformation. The product should be handled with care, so it maintains its original shape prior to insertion. If the insert hydrates before placement slightly below the punctal opening (resembling a trumpet shape), it should be discarded and a new insert should be used. If the insert hydrates before ideal positioning or if a portion of the insert is protruding and unable to be inserted, it should be removed, discarded and a new insert should be used. (Note: cutting of the exposed insert is NOT allowed.)

5. OTX-DED or HV insert can be visualized when illuminated by a blue light source (e.g., slit lamp or hand-held blue light) with yellow filter.

Placement of OTX-DED or HV insert in Canaliculus

The investigator will grade the level of ease of insertion of the ophthalmic insert as “easy” (1), “moderate” (2) or “difficult” (3).

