3. SUBJECT POPULATIONS

3.1. Population Definitions

- Intent-to-Treat (ITT):** The ITT population will include all randomized subjects. Subjects who are randomized but not treated due to procedural screen failures will be included as part of ITT population.
- Modified Intent-to-Treat (mITT):** The Modified ITT will include all subjects in ITT who received the insert in the study eye, investigational product (IP) (OTX-DED or HV). The mITT population will be used as the primary efficacy analysis population and will also be used for all efficacy endpoints. Analyses performed on the mITT population will be according to the treatment the subject are randomized.
- Per Protocol (PP):** The PP population will include all mITT subjects who do not have any major protocol deviation which is likely to seriously affect the safety and efficacy outcomes of the study and who do not report excessive artificial tear use defined as greater or equal to 30 drops between Insertion/Day 1 (Visit 2) and Week 2 (Visit 4). Analysis on the PP population will be used as secondary efficacy analysis and will be performed for select efficacy endpoints, analyzing subjects under the treatment actually received. Important protocol deviations will be identified prior to locking the study database.
- Safety:** The Safety population will include all randomized subjects who received Investigational Product (IP) (OTX-DED or HV). Analyses performed on the Safety population will be according to the treatment the subject actually received.

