4.2.2. Unit of Analysis

Both eyes will be treated with the same treatment/formulation. The study eye and non-study eye will be determined at the time of programing as follows. If both eyes qualify, the eye having the highest (worst) grading score among Nasal, Temporal, and Frontal zones from the photographic assessment of conjunctival hyperemia at baseline will be designated as the study eye and the other eye will be designated as the non-study eye. If both eyes have the same photographic assessment conjunctival hyperemia the highest (worst) grade score, the right eye will be the study eye. If only one eye qualifies, that eye will be the study eye, but both eyes will still receive the same treatment/formulation and be included in the safety analysis. If only an insert is successfully placed in one eye, then that eye will be the study eye, if it qualifies for the study.

The unit of analysis will be the study eye (primary study eye) with the worst zone chosen for bulbar conjunctival hyperemia summaries and analyses. If there are equal scores in two or more zones, the worst zone will be selected in a preferential order with Nasal zone being the most preferred, followed by Temporal zone, and then by Frontal zone. Efficacy summaries will be presented for both study and non-study eyes. Safety summaries will include summaries of both study and non-study eyes. All primary, sensitivity, secondary, and exploratory endpoints will be analyzed for both study and non-study eyes, separately. All summaries will be presented by treatment groups and visits, where appropriate. In addition to looking at the individual formulations, the two formulations of OTX-DED will be combined and summarized.

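### Ease of insertion is compared only where placement succeeded and with a test that ignores grade order, and no by-arm comparison of placement failure is planned

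*SAP*

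**What the plan says.** **Endpoint and scale.** Ease of insertion is an exploratory efficacy endpoint (Protocol 6.2.2.2; SAP 2.6.1.3). Protocol Appendix 11 defines it: "The investigator will grade the level of ease of insertion of the ophthalmic insert as" easy (1), moderate (2) or difficult (3). There is no grade for an insert that could not be placed.

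**Test.** SAP 4.7.4 says that for ease of insertion and "ease of visualization as assessed by the Investigator, the Pearson Chi-squared statistic will be used". The comparisons are each dose against vehicle and both doses combined against vehicle. Insert presence, by contrast, is tested with Fisher's exact test and has confidence intervals.

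**Population.** "The exploratory analyses will be done on mITT populations". SAP 3.1 defines that population: "The Modified ITT will include all subjects in ITT who received the insert in the study eye, investigational product (IP) (OTX-DED or HV"). Two-eye failures stay in ITT only: "Subjects who are randomized but not treated due to procedural screen failures will be included as part of ITT population". Protocol 10.10 had planned ITT for all efficacy endpoints. SAP Section 5 lists the move to mITT and PP for primary, sensitivity and secondary endpoints and does not mention exploratory ones.

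**One-eye failures.** SAP 4.2.2: "If only an insert is successfully placed in one eye, then that eye will be the study eye, if it qualifies for the study". For the return visit, Protocol 8.4.2 says that the "Ease of Insertion Assessment and Tear film PK for the second eye should only be performed if the second eye has a successful insertion".

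**Where failures are reported.** SAP 4.4 counts subjects with neither eye placed as randomised but not treated, and gives disposition events and population counts by treatment group.

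**The concern.** An insert that cannot be placed is the worst result on an insertability scale, and this outcome carries no weight in the comparison meant to describe insertability. If the arms differ mainly in failures, the graded eyes may look alike and the active product will seem as easy to handle as the vehicle.

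The documents' own dimensions make a difference plausible. The vehicle insert is 0.38 mm wide when dry, against 0.41-0.49 mm for 0.2 mg and 0.44-0.55 mm for 0.3 mg. The study exists to supply estimates for later trial designs (Protocol 10.3; SAP 4.1), and an estimate conditional on success would flatter the product for that use.

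Separately, a Pearson test treats easy, moderate and difficult as unrelated labels and so spends power on patterns that are not of interest.

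**Working it through.** The plan gives no power, grade distribution or failure rate for this endpoint, so there is no figure to reproduce. The inputs from the documents are about 50 subjects per arm, two-sided alpha 0.05, three ordered grades, and the dry diameters. All grade and failure rates below are assumptions.

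**1. Can a failed eye enter the study-eye table?**
- Neither eye placed: the subject is outside mITT.
- One eye placed and qualifying: that eye becomes the study eye, so the failed eye is the non-study eye.
- One eye placed but not qualifying: the qualifying eye has no insert, so the subject is outside mITT.

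In no case does a failed study eye enter. SAP 4.2.2 also analyses the non-study eye, but an eye that fails again at the return visit has no grade from that visit.

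**2. Dry diameter relative to vehicle.**
- 0.2 mg: 0.41/0.38 = 1.08 to 0.49/0.38 = 1.29, or 8-29% wider.
- 0.3 mg: 0.44/0.38 = 1.16 to 0.55/0.38 = 1.45, or 16-45% wider.

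**3. Failures only: a constructed table (easy/moderate/difficult/not placed).** Vehicle 35/10/4/1; active 29/8/3/10.
- Planned analysis: 35/10/4 against 29/8/3. The easy share is 35/49 = 71% against 29/40 = 73%. Chi-squared = 0.018 on 2 df, p = 0.99.
- Failure directly: 1/50 against 10/50, Fisher p = 0.008.
- Four categories: Pearson p = 0.04; rank-sum p = 0.085.

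**4. Order only: a constructed table without failures.** 40/8/2 against 30/13/7: Pearson p = 0.067, rank-sum p = 0.023.

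**5. Simulated power, 50 against 50.** Grade percentages are among placed eyes; the last three columns are power.

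| Assumed scenario | Planned Pearson | Rank-sum, placed only | Rank-sum, 'not placed' worst |
|---|---|---|---|
| 80/16/4 v 60/28/12, no failures | 51% | 61% | same |
| 80/15/5 v 60/25/15, no failures | 54% | 64% | same |
| 80/16/4 v 65/25/10, failures 2% v 10% | 31% | 39% | 65% |
| same grades, failures 2% v 4% | about 31% | about 39% | 42% |
| same grades, failures 2% v 2% | about 31% | about 39% | 37% |
| equal grades, failures 2% v 15% | 4% | at null rate | 30% |

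Using order gains 61 − 51 = 10, 64 − 54 = 10 and 39 − 31 = 8 points. The further gain from adding 'not placed' runs from 65 − 39 = 26 points down to 37 − 39 = −2, depending wholly on the assumed failure rates. In the last row, Fisher's test on failure has about 50% power, well above the four-category rank test.

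**6. Sparse cells.** Expected counts below 5 are common (3.1 and 3.9 for 'difficult' in step 3). Under the null the planned test rejected about 4% of the time, so sparsity did not inflate error.

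**The case against.** **Failures are not hidden from the report.** Disposition shows two-eye failures and population counts by arm, so a large imbalance in two-eye failure would be visible. A reader might infer that the hardest insertions disappear altogether; the documents do not support that. What stands is that disposition is descriptive, and that one-eye failures have no specified by-arm table.

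**Failed first attempts may still be graded.** The success condition in Protocol 8.4.2 governs the return visit. Whether a failed Day 1 attempt gets a grade is unclear rather than excluded. An eye placed at the return visit (Visit 2B in SAP 4.7.4) stays in the analysis. This stands.

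**An arm difference is not established.** The placement technique dilates the punctum first, and no failure rate is given. The diameters show only that a difference is plausible.

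**Ease of visualization.** One might extend the argument and score an insert that is no longer visible as the worst visualization grade. That would be wrong. The insert is designed to soften and clear (Protocol 4.2), so absence at later visits can be the intended result, and presence is already tested at every post-baseline visit.

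**Materiality.** The endpoint is exploratory, the study is not powered, and counts and percentages are shown whatever the test. The protocol named the same test in advance. All of this stands and limits the weight of the point.

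**Conclusion.** The point holds in a limited form. The study-eye comparison of ease of insertion is conditional on successful placement, and its test ignores an order that the scale plainly has. No comparison of placement failure is planned, and one-eye failures have no by-arm table. A difference in insertability could therefore be missed or understated.

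The loss from ignoring order is about 8-10 power points at 50 per arm under the assumed distributions. The loss from leaving out failures cannot be sized from the documents: it is nil if failure rates are equal and nearly total if the arms differ only in failure. Two stronger inferences fail. A large overall power gain cannot be claimed, because most of it comes from the failure rates one chooses to assume. Nor do small expected counts make the chi-squared test invalid here, since its null rejection stayed near 4%. No primary or secondary conclusion is affected, and the change is a minor improvement.

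**What to change.** 1. **Placement failure.** In all randomised subjects with an attempted insertion, tabulate by arm the number with one eye and with neither eye finally placed. Compare failure for each dose and the combined doses against vehicle with Fisher's exact test and a confidence interval for the difference. Use the subject as the unit, since two eyes of one person are not independent. The Fisher and Chan-Zhang code in SAP 7.1.6 can be reused.
2. **Ease of insertion.** Replace Pearson chi-squared with a Wilcoxon or CMH row-mean-score test, exact if sparse. As at least a supporting analysis, add 'not placed' as the worst category. Choose the eye without regard to placement, or take the worse eye, because the SAP 4.2.2 reassignment rule would otherwise remove one-eye failures again. This does not replace item 1, which is stronger when only failure differs.
3. **Wording.** State whether a failed Day 1 attempt is graded and which grade counts when both Visit 2 and Visit 2B have one. List the mITT choice for exploratory endpoints in SAP Section 5.
4. **Ease of visualization.** Add no 'not visible' grade. State that the result is read alongside insert presence.

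The cost is one derived category, one extra table and a few lines of SAP text. Placement status is already needed to define mITT, so no new data collection is required for items 1 and 2.
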